4.1 INCLUSION CRITERIA

Subjects must meet all of the following inclusion criteria to qualify for enrollment into the study:

1. All subjects will be 22 – 65 years of age
2. Major Depressive Episode Diagnosis, Severity, and Duration:
 - a. Subjects will meet the DSM-IV-TR primary diagnosis of initial or recurrent Major Depressive Disorder by DSM-IV-TR criteria rendered by structured interview using the Mini International Neuropsychiatric Interview (MINI).
 - b. HAM-D₁₇ total score ≥ 17 and Item 1 score greater than or equal to 2 at Screen and Baseline visits.
 - c. HAM-D₁₇ total score decrease of 5 or fewer points between Screen and Baseline visits.
 - d. Duration of current episode ≥ 8 weeks. The definition of an episode is demarcated by a period of ≥ 2 months when the subject met full criteria for the DSM-IV-TR definition of Major Depressive Episode. Maximum duration of current episode cannot exceed 2 years.
3. Subjects have not responded adequately to at least one antidepressant medication in the current episode, with dose and duration defined as minimum confidence level 3 on the Antidepressant Treatment History Form (ATHF).
4. The baseline EEG is of sufficient duration and quality that it can be processed for quantitative analysis and determination of a valid IAF.
5. Subjects are willing and able to adhere to the intensive treatment schedule and all required study visits.

4.2 EXCLUSION CRITERIA

Subjects will be excluded from study participation if one of the following exclusion criteria applies:

1. Subjects are unable or unwilling to give informed consent.
2. Diagnosed with the following conditions (current unless otherwise stated):
 - a. Any other current primary Axis I mood, anxiety, or psychotic disorder, including bipolar disorder.
 - b. Depression secondary to a general medical condition, or substance-induced.
 - c. History of substance abuse or dependence within the past 6 months (except nicotine and caffeine).
 - d. Any bipolar disorder or psychotic disorder (lifetime), including schizoaffective disorder, or major depression with psychotic features in this or previous episodes.
 - e. Eating disorder (current or within the past year).
 - f. Obsessive compulsive disorder (lifetime).
 - g. Post-traumatic stress disorder (current or within the past year).
 - h. ADHD (currently being treated).
3. Subjects meeting criteria for Axis II cluster A or B diagnosis based upon DSM-IV TR criteria, which in the judgment of the Investigator may hinder the subjects in completing the procedures required by the study protocol.
4. Subjects with a clinically defined neurological disorder including, but not limited to:
 - a. Any condition likely to be associated with increased intracranial pressure.
 - b. Space occupying brain lesion.
 - c. Any history of seizure EXCEPT those therapeutically induced by ECT (childhood febrile seizures are acceptable and these subjects may be included in the study).
 - d. History of stroke.
 - e. Transient ischemic attack within two years.
 - f. Cerebral aneurysm.
 - g. Dementia.
 - h. Mini Mental Status Exam (MMSE-2) score of ≤ 24 .
 - i. Parkinson's disease.
 - j. Huntington's disease.
 - k. Multiple sclerosis.
 - l. Increased risk of seizure for any reason, including prior diagnosis of increased intracranial pressure (such as after large infarctions or trauma), or currently taking medication that lowers the seizure threshold. Medications that lower the seizure threshold are included in the Prohibited Concomitant Medication (Section 5.8).
 - m. Any history of traumatic brain injury with loss of consciousness ≥ 30 minutes
5. Subjects who are currently hospitalized due to severity of depression symptoms.
6. Subjects with any of the following treatment histories:
 - a. TMS treatment within 6 months prior to the screening visit.
 - b. Lifetime history of treatment with sTMS therapy.
 - c. ECT treatment within 1 year prior to the screening visit.
 - d. Failure to respond to TMS or ECT treatment (i.e., consistent with ATHF confidence level 3 or higher) in this or any previous episode.
 - e. Lifetime history of treatment with Deep Brain Stimulation or Vagus Nerve Stimulation.
 - f. Participation in any investigational drug or device trial within 6 months of the randomization visit.
 - g. Subjects who have been treated with fluoxetine within the past four weeks.
 - h. If participating in psychotherapy, must have been in stable treatment for at least 2 months prior to entry into the study, with no anticipation of change in the frequency of therapeutic sessions, or the therapeutic focus over the duration of the trial.

7. Use of any medication(s) listed on the Prohibited Concomitant Medication (Section 5.8) within 1 week of randomization.
8. Subjects are adequately benefiting from current antidepressant medication(s).
9. Significant acute suicide risk, defined as:
 - Greater than or equal to 1 suicide attempts in the past 12 months; or
 - Has a clear-cut plan for suicide and states that he/she cannot guarantee that he/she will call his/her regular psychiatrist or the Investigator if the impulse to implement the plan becomes substantial during the study; or
 - In the Investigator's opinion, is likely to attempt suicide within the next 6 months.
10. Cardiac pacemakers, implanted medication pumps, intracardiac lines, or acute, unstable cardiac disease.
11. Intracranial implant (e.g., aneurysm clips, shunts, stimulators, cochlear implants, stents, or electrodes) or any other metal object within or near the head, excluding the mouth, which cannot be safely removed.
12. Clinically significant abnormality or clinically significant unstable medical condition, as indicated by medical history, physical examination, ECG results, or clinical laboratory testing, that in the Investigator's judgment might pose a potential safety risk to the subject or limit interpretation of the trial results, e.g., any uncontrolled thyroid disorders, hepatic, cardiac, pulmonary and renal malfunctioning.
13. Women who are currently pregnant or not using a medically acceptable means of birth control and women who are breastfeeding.
14. Positive urine drug screen for illicit substances. (A positive urine drug screen at screening may be repeated once prior to randomization).
15. Any condition which in the judgment of the Investigator would prevent the subject from completion of the study.

5 STUDY PROCEDURES

5.1 SUBJECT SCREENING AND ENROLLMENT

Prior to recruitment of any subjects into the study, written approval of the protocol and informed consent must be obtained from the Institutional Review Board (IRB) or Ethics Committee (EC).

Subjects interested in participating in this clinical trial will be assessed for eligibility. If a potential participant is found to be eligible for enrollment, the study consent form will be reviewed with the subject and the study methods and requirements will be explained. Written informed consent will then be obtained. A pre-screening log will be maintained for all subjects who are screened for enrollment but either do not qualify or decide not to participate in the study.

Once a subject has been consented, the screening process will begin. For each subject this will include verification of their ATHF for the current episode of depression. Verification consists of a detailed interview with the patient to obtain history of illness and treatments. When possible, and with the subjects permission, verification may be supplemented by a phone interview with the subject's attending physician/psychiatrist and a full review of the subject's medical records of present history, including pharmacy records.

A copy of the signed consent form will be provided to the study participant and the original signed consent form will be maintained in the subject's files.

The Screening and Baseline assessments will be split by at least 7 days. Screening visits maybe performed before an antidepressant medication washout period (if applicable), while Baseline visits must be post-washout, which will be done at least one week following screening but before randomization. The HAM-D₁₇ assessment conducted at screening will be confirmed by independent review to determine eligibility (HAM-D₁₇ greater than or equal to 17). The Baseline visit clinical assessment results will then be used as the baseline values for the study. Subjects must meet eligibility requirements at both Screening and Baseline visits and not show improvement of >5 points between these visits to remain eligible for randomization in the study.

5.2 ASSIGNMENT OF SUBJECT IDENTIFICATION

Once a subject has consented to enrollment in the study, a sequential Subject Identification (SubID) Number will be assigned. This number will consist of the following format: NNDXXXX-XXX-XXX. The first

7 letters/digits represent the protocol number, the next three digits represent the pre-assigned site number, and the last three digits represent the numerical sequence of enrollment, such that the first study subject at any site will be "001," the second "002" etc. The first enrolled subject for this trial at Site 1, for example, will be assigned SubID number NND3002001001.

The SubID number is to be recorded on all study documents and will link the study treatment and the study documents to the subject's name and medical record. To maintain confidentiality, the subject's name should not be recorded on any study document other than the informed consent form.

5.3 RANDOMIZATION AND BLINDING

This study is randomized, double-blind, and sham-controlled to minimize bias. Subjects will be randomized following the post-washout baseline assessment (Day 0) to one of the two treatment groups (sTMS vs. sham treatment), at a 1:1 ratio. Randomization will be stratified by site in blocks of 10 determined by a computer generated randomization table defined prior to the start of the trial. Each site will be given a set of 10 randomized PPMs. The assignment is determined by a computer generated randomization table defined prior to the start of the trial. Each Patient Passport Module (PPM) has a 128-bit number preprogrammed for use with a corresponding active or sham device. This number is independent of the Subject ID or device serial number, and is not shown on the PPM or displayed by the device. It is impossible to determine if the PPM is to be used with an active or sham device just by looking at the number. Instead, the software embedded in the device reads the number and uses a decoding algorithm to determine if the PPM is to be used with that particular device. If not, the device will inform the user that the PPM is not valid for that device. The decoding algorithm is kept with the manufacturer, and is not known by the clinical site or any clinical monitor.

These PPMs are labeled with a sequential number to maintain the blinding. At the time an individual subject is randomized, the site will select the next PPM in the instructed numerical order and assign it to that subject. Each site will keep a log of the PPM number assigned to each subject. (See Section 6 for additional information on the PPM). Investigators who perform the assessments, those administering treatment, and subjects who participate in the trial will be blinded to study treatment. A Treatment Blinding Questionnaire will be completed by those performing the assessments, those administering treatment, and subjects at the Week 1 and Week 6 Evaluation Visits for sponsor review to ensure the blind is maintained.

Both the active and sham sTMS devices have the same outer structure and motor functions, and will look, sound and operate in a similar fashion in order to maintain blinding of the treatment. However, the sham devices will not deliver the alternating magnetic fields that the active device produces. Besides a subtle mechanical vibration, neither active nor sham device will produce any physical sensation. The trial equipment will be labeled with serial numbers that indicate whether they are active or sham. The treatment site will be kept blind of the assignment code.

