Qualified subjects will be randomized to either active sTMS or sham treatment groups in a 1:1 ratio on an individual basis. Randomization will be stratified by site in blocks of 10 determined by a computer generated randomization table defined prior to the start of the trial. Each site will be given a set of 10 randomized PPMs. Treatment will be initiated on Day 1 of the study. Subjects will come to the clinic for 5 daily treatment sessions for a total of 6 “treatment” weeks. A visit interval of 5-10 calendar days has been set for each “treatment” week to accommodate visit scheduling flexibility. Treatment will be discontinued at the end of Week 6 (30 treatment sessions). Subjects will be clinically evaluated for safety and efficacy at the end of each of the six weekly treatment courses.

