7.3 CLINICAL PARAMETERS BY VISIT

Initial Screening/Baseline Visit

Potential study participants will be screened for eligibility per the protocol eligibility criteria. The Screening/Baseline visits may be split into two or more days. After informed consent has been signed and washout from previous medications is complete (when necessary), the following assessments will be performed as part of the subject eligibility assessment:

- MINI
- ATHF
- Mini Mental Status Exam (MMSE-2)
- Medical and psychiatric history
- Concomitant medication history
- Adverse Events
- Demographics
- NeoSync EEG
- Vital Signs (HR, BP)
- Weight
- Pregnancy Test (HCG)
- Urine Toxicology Screen
- HAM-D/MADRS
- IDS-SR
- C-SSRS
- Standard 12 lead ECG (optional)
- Physical Examination (optional)
- Laboratory Assessments (optional)

Randomization into the Trial

Upon successful completion of Screening and Baseline visits to establish eligibility, subjects will be randomized into the trial. A PPM will be selected and assigned to the subject. This PPM can only be used with either an active or sham device as they are already encrypted and assigned to a randomization arm per the pre-generated randomization schema. The subject's EEG will be recorded. The EEG will be

processed and used to determine the treatment parameters stored on the subject's PPM. The PPM should be labeled with the Sub ID. That PPM must be used with that device for all treatments.

Double-Blind Treatment Visits (Week 1-6)

After the subject has been deemed to be acceptable for inclusion in the trial and randomized to a treatment group, they may begin scheduled treatments. They will go to the physician's office 5 days per treatment week to complete the treatment procedure. In addition, subjects will be assessed for changes in adverse events, concomitant medications, or worsening of symptoms that may need physician intervention at each of the treatment visits. The first treatment visit may occur after randomization at the baseline visit given sufficient time.

Double-Blind Evaluation Visits (Week 1-5)

In addition to the treatment visits, an evaluation will be conducted on the same day as the last treatment (5th treatment session, within 10 calendar days) of each weekly treatment cycle. The following assessments will be performed as part of that evaluation:

- HAM-D/MADRS
- IDS-SR
- C-SSRS
- Adverse Events
- Concomitant Medications
- Treatment Blinding Questionnaire(s) (Week 1)

Week 6 /Early Termination Visit

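### Allocation concealment is weak at the level of the coded device: sites hold PPMs already tied to an arm, the device reports a mismatch, and no control against early testing is described

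*Protocol*

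**What the plan says.** **Supply and order.** Protocol Section 5.3: "Each site will be given a set of 10 randomized PPMs". Each is programmed in advance: "Each Patient Passport Module (PPM) has a 128-bit number preprogrammed for use with a corresponding active or sham device". Section 7.3 describes the PPMs, at the moment one is selected, as "already encrypted and assigned to a randomization arm per the pre-generated randomization schema". When a subject is randomized, "the site will select the next PPM in the instructed numerical order and assign it to that subject".

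**Mismatch message.** Section 5.3 says of a PPM that does not belong to the device: "If not, the device will inform the user that the PPM is not valid for that device". Section 6.4 adds that the signal is both audible and visible. It words the lock-out as operating once the PPM has been assigned to a subject. Sections 5.3 and 7.3 contain no such condition.

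**Blocks.** Section 3: "Randomization will be stratified by site in blocks of 10". Section 5.3 repeats this, and the ratio is 1:1. The SAP (Randomization) gives the ratio and stratification by center, without a block size.

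**Safeguards stated.** The PPM's internal number is not visible, and the decoding algorithm stays with the manufacturer (Section 5.3). Active and sham devices look and sound alike, and the site does not hold the key to the serial numbers (also Section 5.3). The site logs which PPM went to which subject. No sealed pack, central release or log of insertions is described. Section 6.4 mentions stored usage data only for therapy sessions.

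**The concern.** Allocation concealment means that whoever decides on enrolment cannot foresee the next assignment. Here the assignment sits in a numbered object at the site, and the study device can sort those objects into two groups. The stated safeguards hide which group is active. They do not hide which group the next subject will join.

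This matters because the mapping from device to arm is the same for every subject. Staff who come to believe that one device is active, through an unblinding or through impressions of past subjects, hold that belief for every later PPM they can match to a device. They could then delay, hurry or decline enrolment according to the coming device. Selection at entry of this kind is not corrected by the randomization list and cannot be detected by Fisher's exact test on Week 6 response. The trial is small (92 evaluable subjects planned) and is meant to be confirmatory.

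**Working it through.** The plan gives no figure for predictability, so there is none to reproduce.

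**1. Can the next PPM be tested?**

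| Question | Section 5.3 | Section 7.3 | Section 6.4 |
|---|---|---|---|
| Is the arm fixed before assignment? | Yes, preprogrammed | Yes | Not contradicted |
| Does a wrong device respond? | Yes, no condition stated | PPM fits only one device type | Yes, worded as after assignment |

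On the reading of Sections 5.3 and 7.3, inserting the next unassigned PPM shows which coded device it fits, every time. On the narrow reading of Section 6.4, the check may not run yet. The documents do not settle this.

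**2. What can be guessed without testing?**

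Inputs: blocks of 10 within site, 1:1, so m = 5 per device type (Protocol Sections 3 and 5.3); 120 enrolled (Section 11.4); up to 16 sites (Synopsis). Assumptions: staff can see which coded device each past subject used, and they guess the type with more PPMs left, tossing a coin when the two are level. There are C(10,5) = 252 equally likely sequences.

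*Full block:*
- Expected number certain at the end of the block: 2m/(m+1) = 10/6 = 1.67 of 10 (16.7%).
- Expected correct guesses: m + (4^m/C(2m,m) − 1)/2 = 5 + (1024/252 − 1)/2 = 6.53 of 10 (65.3%, against 50% by chance).

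*Part block:* with equal enrolment, 120/16 = 7.5 subjects per site, so take 7 and 8.
- Chance that some assignment is certain by the 7th subject: one type must be used up within the first 6, so 2 × C(6,5)/252 = 12/252 = 4.8%.
- By the 8th: 2 × C(7,5)/252 = 42/252 = 16.7%.
- Expected number certain in the first 7: (2 + 12)/252 = 0.056, or 0.8% of assignments. In the first 8: (2 + 12 + 42)/252 = 0.222, or 2.8%.
- Correct guesses, by enumerating all 252 sequences: 4.09 of 7 (58.4%) and 4.81 of 8 (60.1%).

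*Range:* 16 sites is a maximum. If enrolment is raised to 240, the average is 240/16 = 15 per site, which passes a full block.

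**3. Would smaller, varied blocks help?**

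In a simulation where the guess is always the device used less often so far at the site, random blocks of 4 and 6, or of 4, 6 and 8, give 66% to 68% correct at 8 and 10 subjects per site. Fixed blocks of 10 give 60% to 65%. Small varied blocks remove certainty at the block's end, but make the next device easier to guess.

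All these percentages refer to the coded device, not to active or sham.

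**The case against.** The strongest reply is that a mismatch message reveals a label, not a treatment. With the decoding algorithm and serial-number key withheld and the devices alike, the arm remains a 50:50 guess until someone is unblinded, which Section 5.5 expects to be rare, or draws a correct inference. This stands. A reader might infer that the site can learn the next subject's arm, or that concealment is lost outright. The documents do not support either.

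Second, testing a PPM early departs from the written procedure. A PPM is taken only when a subject is randomized, after Screening and Baseline are complete, and the screening EEG uses a separate generic PPM. This also stands: the gap is a missing safeguard against misuse, not a fault triggered by following the protocol. Nor is PPM packaging described, so the absence of seals is read from silence. One qualification is that the baseline EEG is an inclusion criterion (Section 4.1), yet it is recorded on the assigned PPM after randomization (Section 6.4). One eligibility step therefore falls after the device is known even when every rule is kept.

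Third, bias requires staff to form a belief and act on it, and mistaken beliefs need not point the same way at different sites. That is fair, and no size of bias can be given. Independent confirmation of the screening HAM-D (Section 5.1) narrows the room for selection. The blinding questionnaire, which the SAP says records how the machine operated as a possible reason for a guess, could show afterwards that beliefs had formed. Neither conceals the next assignment.

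**Conclusion.** Concealment of the coded device is weak; concealment of active versus sham is protected, but only for as long as nobody at the site learns or infers the arm of one device. After that, the fixed mapping extends the knowledge to every PPM that can be matched to a device there.

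The readable PPM is the main weakness. A reader might infer that every coming allocation is known in advance. That holds only at device level, only through an off-procedure insertion, and only if the check runs on an unassigned PPM, which Section 6.4 leaves open.

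The printed block size is secondary. The figures of 65.3% guessed and 16.7% certain apply to a completed block. At 7 to 8 subjects per site they fall to 58% to 60% guessed and 0.8% to 2.8% certain. These rest on equal enrolment across 16 sites and on staff being able to tell the devices apart by serial number; fewer sites, or an increase in sample size, would move them toward the full-block values.

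**What to change.** 1. Supply PPMs in opaque, tamper-evident, numbered packs. Open a pack only after eligibility is signed off and the subject is logged as randomized. Record the opening time, and check the seals at the existing monitoring visits. Because the baseline EEG needs the assigned PPM, the sign-off must cover every criterion except that one.
2. Remove the block size and the number of PPMs per set from the protocol text given to sites. This cannot undo what sites have already read.
3. Reconcile Section 6.4 with Sections 5.3 and 7.3, stating whether a device responds to a PPM that has not yet been assigned.
4. If block sizes are varied for sets not yet shipped, do not use mainly smaller blocks, for the reason shown in the working.

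The cost is packaging work, protocol wording and, if blocks are varied, a regenerated list and a less regular PPM supply. Endpoint, sample size and treatment are unchanged. Sealed packs close the testing route but leave the guess from past device use, so item 1 is the main remedy and not a complete one.
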